This is a 3-group, 6-session, randomized outpatient study in which drinkers are given access to a beverage that does or does not contain alcohol and are presented with cues that are or are not alcohol-related. For the US (unconditioned stimulus) version of the retrieval-extinction procedure, drinking provides the retrieval experience, which occurs before the cues are extinguished.

The three experimental groups are determined by whether the retrieval and/or extinction procedures involve alcohol versus control stimuli: (1) alcohol retrieval / alcohol extinction (experimental group) (2) soft-drink retrieval / alcohol extinction (control group A) and (3) alcohol retrieval / soft-drink extinction (control group B). Although soft drinks may have appetitive motivational properties of their own (Berns et al., 2001), we will use the soft drinks as inactive conditions as concerns craving for alcohol: the soft-drink retrieval condition is a no-alcohol retrieval condition, and the soft-drink extinction condition is a no-alcohol extinction condition. Using a soft drink rather than plain water allows for better matching of the sensory salience and caloric content of the alcoholic beverages, and by picking particular beverages (see below) we can minimize the potential for associative overlap between the soft drink and alcoholic beverages. We considered several other control groups, but practical considerations forced us to limit our choices to what was necessary for basic interpretability of the findings.

EMA/GMA data will be collected via smartphone throughout the study. After giving written informed consent in the first visit, participants will be trained to use smartphones for real-time self-report.

In the first laboratory session, scheduled as soon as possible after enrollment, participants will provide information needed for our development of personalized imagery scripts, which we will use in subsequent sessions to induce craving.

Approximately 7 days later, participants will have the first of four retrieval-extinction sessions in which they drink beverages and undergo cue exposure/extinction. These four sessions will be spaced at least 2 days apart from each other.

Abbreviated Title: Lab/GMA drinking

Version Date: 2/16/2022

[figure not shown]

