Approximately 7 days after the last retrieval-extinction session, we will test participants' responses to alcohol cues using two Pavlovian procedures, renewal and reinstatement, that have previously been used in studies of laboratory animals to differentiate the effects of retrieval-extinction from extinction alone (Luo et al., 2015). At this visit, participants will return their smartphones.

Each participant will receive a follow-up phone call approximately 30 days after his or her last visit.

The study will take each participant approximately 3 months to complete, depending on how close together sessions can be scheduled. Each type of session is described in more detail in the Study Procedures section.

2. Study procedures

Study Timeline

Session	Beverage	Empty Packaging	Cue Script	Drinking
2-5. Retrieval	X	X	-	X
2-5. Extinction	X	X	X	-
6. Renewal, same room	X	X	X	-
6. Renewal, different room	X	X	X	-
6. Reinstatement, same room	X	-	-	X

Experimental groups and randomization

As we mentioned above, we needed to limit the number of groups for practical reasons. Participants will be randomized to one of three groups: (1) alcohol retrieval / alcohol extinction, (2) soft-drink retrieval / alcohol extinction, and (3) alcohol retrieval / soft-drink extinction. The use of these two control groups (groups 2 and 3) assesses whether the retrieval-extinction procedure requires both its retrieval component and its extinction component. Group 2 represents a traditional CET approach, with

Abbreviated Title: Lab/GMA drinking

Version Date: 2/16/2022

no relevant retrieval procedure. Group 3 controls for mere alcohol exposure in the laboratory, which has actually been shown to have some effect on subsequent drinking (Hodgson & Rankin, 1976; Modell et al., 1993; Pratt & Davidson, 2005).

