We describe the content of EMA questionnaires in a separate section below, after the description of the sessions.

Abbreviated Title: Lab/GMA drinking

Version Date: 2/16/2022

b. Sessions 2-5: Retrieval-extinction sessions

BAC will be checked at the start of each session and will need to be 0.00% to proceed. Session 2 will be scheduled 2-3 days after Session 1, with 2-3 days separating each subsequent session. Under unusual circumstances, sessions might be separated by up to 10 days. Unusual circumstances would include, for example, staff shortages or unforeseeable participant emergencies that combine with Federal holidays or weather events. We expect such scheduling to be rare and will not present it in the consent form as an option. Participants will be terminated from the study as unable or unwilling to complete study measures if they cannot schedule a retrieval-extinction session within this 10 day window.

At the beginning of Session 2, participants will complete a timeline follow-back calendar (Sobell et al., 1979; Sobell et al., 1996a) covering the time between Session 1 and Session 2 to provide a retrospective report of drinking at “baseline” for comparison with that week’s GMA reports. At the beginning of Session 3-5, participants will report on their drinking in the time since their previous experimental session.

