Approximately 30 days after the final laboratory session, we will call the participant to conduct a timeline follow-back calendar (Sobell et al., 1979; Sobell et al., 1996a) and to administer the Penn Alcohol Craving Scale (Flannery et al., 1999). We will then disclose the design of the study to them, explain which experimental group they were in, and debrief them about their perceptions of the study (e.g., whether they had known that they were in a control group or the intervention group).

Following the experimental debriefing, the participant will be asked to speak to a master's-degree-level counselor about his or her drinking behavior. The counselor will provide advice consistent with participants' AUDIT scores (Babor et al. 2001, p. 20) and, when appropriate, referrals to treatment programs and support groups for alcohol-use disorders.

The same advice will be given to study candidates who score in the same range (8-15) on the AUDIT but who are disqualified from study participation for other reasons, such as not endorsing any AUDIT items beyond the first three. This would be done by screening staff toward the end of screening, rather than in a post-study follow-up.

Physiological monitoring during Session 2-6

We will continuously measure heart rate, blood pressure, skin conductance, and skin temperature during the extinction procedures in Sessions 2-5 and during the tests for renewal and reinstatement in Session 6. We will use these measurements to assess changes in participants' physiological responses to the alcohol and soft-drink cues within and between sessions. Physiological measurements will be obtained using a standard laboratory physiological monitoring system: a BIOPAC or Coulbourn Instruments LabLinc noninvasive blood pressure amplifier with CNAP Monitor arm and finger cuffs plus fingertip-mounted skin temperature and conductance sensors. We have used these systems to measure participants' physiological responses to drug and stress cues (NIDA IRP protocols 020, 475).

Geographical Momentary Assessment (GMA) data collection

GMA data collection will begin with the issuing of a smartphone in Session 1 and conclude at the beginning of Session 6, the final laboratory visit. Before being issued a smartphone, each participant will have an instructional session in which the assessment items and smartphone operation are explained.

EMA Entries

Participants will make the following types of entries:

Event-contingent (EC) entries:

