Co-primary outcome 2: Reduction of craving and drinking in daily life. This will be analyzed in multilevel models, with the dependent variable operationalized in terms of participants' changes in alcohol craving and alcohol drinking in GMA reports after the four extinction-retrieval sessions, controlling for any preexisting differences. Because we cannot predict the time course of differential changes, our main analyses here will omit GMA data from the period when the four extinction-retrieval sessions are occurring. The dependent variable will be daily frequency of craving reports (or, in a separate analysis, daily number of drinks); the independent variables will be coded the same way as in the models for co-primary outcome 1, with experimental group (3 levels) dummy-coded so the experimental group is the reference level and a Wald test of joint significance can assess whether the experimental group differs simultaneously from both control groups. The continuous covariate will be each participant's overall frequency of craving or drinking during the baseline week of GMA.

Depending on the distribution of the dependent variable, we will use either general linear mixed models (e.g., SAS Proc Mixed) or generalized linear mixed models (e.g., SAS Proc Glimmix or SAS Proc NLMixed)—each of which provides a repeated-measures analysis that can handle missing days or early dropout and can accommodate person-level covariates, which will be included if they improve the fit of the model. These models use maximum-likelihood estimation and allow for specification of an

Abbreviated Title: Lab/GMA drinking

Version Date: 2/16/2022

autoregressive error structure (which can be tested against alternative error structures to provide the best-fitting model). In supplementary analyses, we will examine the time course of any differences that emerge during the period when the four extinction-retrieval sessions are occurring.

Secondary outcomes: Most of the other laboratory measures, such as self-reported craving and drinking at the 30-day follow-up visit, urine biomarkers for drinking, and heart-rate responses to cues, will be analyzed by an ANCOVA approach similar to the one used for the co-primary outcome measure 1. Analysis of the GPS component of the GMA data will be more exploratory, but will include testing for group differences in susceptibility to alcohol craving as a function of nearness to bars and liquor stores—a possible reflection of cue reactivity.

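### The procedures section sets Session 2 only 2-3 days after Session 1, although the overview says about 7 days and the analysis of co-primary outcome 2 adjusts for a baseline week

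*Combined protocol and SAP*

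**What the plan says.** The protocol gives two intervals for the same step.

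- Section E.1 (Study overview), following the description of Session 1: "Approximately 7 days later, participants will have the first of four retrieval-extinction sessions".
- Section E.2.b (Sessions 2-5): "Session 2 will be scheduled 2-3 days after Session 1, with 2-3 days separating each subsequent session". Gaps of up to 10 days are allowed, but only in unusual circumstances that are expected to be rare.

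Other text assumes a week. In E.2.b itself, the drinking calendar covering Sessions 1 to 2 is collected "for comparison with that week’s GMA reports". In section I.2, the covariate for co-primary outcome 2 is each participant's "overall frequency of craving or drinking during the baseline week of GMA".

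Two further statements fix which data can serve as baseline. Section E.2 (GMA data collection) says "GMA data collection will begin with the issuing of a smartphone in Session 1 and conclude at the beginning of Session 6". Section I.2 says "our main analyses here will omit GMA data from the period when the four extinction-retrieval sessions are occurring".

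**The concern.** The Session 1 to Session 2 gap is the whole GMA baseline for co-primary outcome 2. Nothing is collected on the phone before it, and the data after it are excluded until treatment ends. Staff who schedule from E.2.b would therefore supply 2-3 days of baseline where the analysis expects seven. For drinking it is less still: section E.2 asks for 24 hours without alcohol before each session, which leaves about 1-2 unrestricted days. A window that short also cannot cover a weekly cycle, whereas the follow-up period is a week.

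Section D says that effects on the daily-life measures alone would count as sufficient evidence of efficacy, so this outcome carries real weight. A shorter baseline makes the covariate noisier, so it removes less between-person variance and corrects less for chance imbalance.

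**Working it through.** **Can the text settle the interval?** Section E.1 says "The study will take each participant approximately 3 months to complete, depending on how close together sessions can be scheduled". Counting days:

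- E.2.b schedule: (2 to 3) + 3 × (2 to 3) + 7 = 15-19 days from Session 1 to Session 6, and 45-49 days with the 30-day call.
- E.1 schedule, with 2-3 days between later sessions: 7 + 3 × (2 to 3) + 7 = 20-23 days, and 50-53 days with the call.

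Both fit within about 3 months, so that sentence does not decide. The overview figure is not shown in the copy reviewed.

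**The plan's own power figure.** Section J gives power .80 for f² = 0.13 with 75 participants. A noncentral F calculation (2 tested predictors, 3 in total, 71 denominator df, noncentrality 0.13 × 75 = 9.75) gives 0.787. Power of exactly .80 needs f² = 0.134, which rounds to 0.13, so the figure reproduces. Because f² is set directly, the number of baseline days does not enter it.

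**Precision loss.** Inputs from the documents: 7 baseline days (E.1, I.2) or 2-3 (E.2.b); one week of follow-up (A. Précis); 75 completers (J). Inputs assumed because the documents do not give them: day-level intraclass correlation (ICC) .3 (range .2-.4); correlation ρ between a person's true baseline and follow-up levels .7 (range .5-.9); day-to-day autocorrelation φ of 0, .2 or .4. Section I.2 permits an "autoregressive error structure (which can be tested against alternative error structures to provide the best-fitting model").

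With day-level variance 1, b = ICC, w = 1 − ICC, k baseline days and m follow-up days:

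- g(k) = [k + 2 Σ (k − l) φ^l] / k², summed over l = 1 to k − 1; this equals 1/k when φ = 0.
- Adjusted variance V(k) = b + w·g(m) − (ρb)² / [b + w·g(k)].

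Craving with independent days and m = 7, so b + w·g(7) = .3 + .7/7 = .4 and (ρb)² = .21² = .0441:

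- V(7) = .4 − .0441/.4 = .2897
- V(3) = .4 − .0441/.5333 = .3173; ratio 1.095
- V(2) = .4 − .0441/.65 = .3322; ratio 1.146

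Variance ratios at central values, with the range over the assumed ICC and ρ in brackets. Craving is compared with a 7-day baseline. Drinking is compared with 6 non-abstinence days, with m = 6.

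| φ | Craving, 3 days | Craving, 2 days | Drinking, 2 days | Drinking, 1 day |
|---|---|---|---|---|
| 0 | 1.095 (1.037-1.232) | 1.146 (1.054-1.373) | 1.122 (1.044-1.308) | 1.199 (1.066-1.538) |
| .2 | 1.078 (1.028-1.191) | 1.114 (1.039-1.288) | 1.093 (1.031-1.233) | 1.139 (1.044-1.369) |
| .4 | 1.056 (1.019-1.139) | 1.078 (1.025-1.197) | 1.062 (1.019-1.156) | 1.088 (1.027-1.231) |

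For craving, the standard error rises by the square root of the ratio: 3-5% with 3 days and 4-7% with 2. Equivalent completers are 75/ratio: 68.5 to 71.0 with 3 days and 65.4 to 69.6 with 2.

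The result is sensitive to ρ. If ρ = 1 (person-level means perfectly stable apart from day-to-day noise), ICC .3 and independent days give ratios of 1.32 and 1.49.

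**The case against.** The strongest reply is that the GMA baseline is not the only pre-treatment information. Section I.2 allows person-level covariates that improve model fit. Screening collects a 90-day drinking calendar (section L.4), and Session 1 collects the Penn Alcohol Craving Scale (E.2.a). Suppose one such covariate correlates .5-.8 with the true baseline level, which is a further assumption. With independent days, the craving loss then falls from 10% and 15% (3 and 2 days) to 4-8% and 5-12%. The drinking loss falls from 12% and 20% (2 and 1 days) to 4-10% and 6-15%. With φ = .4 all are about 2-6%. This is a fair point and lowers the likely loss. But inclusion depends on fit, and the reduced figures are still losses of the same modest order.

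Three other points deserve weight. The correlations are not in the documents, so the size is uncertain in both directions. Actual gaps may exceed the nominal 2-3 days, since sessions can be rescheduled, but 2-3 days is the written rule. And a noisier covariate does not make a false efficacy claim more likely. None of these resolves the contradiction.

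**Conclusion.** The concern holds. E.2.b's interval conflicts with E.1, with its own reference to a week of reports, and with the baseline week in I.2. Followed as written, it leaves 2-3 days as the only GMA baseline for co-primary outcome 2.

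The consequence is a modest loss of precision. There is no bias in the randomized contrast and no error in the stated power. Central estimates are 6-15% more adjusted variance for craving and 6-20% for drinking, and less if the optional covariates enter the model. Confidence is high in the contradiction and in the direction of the effect. The size rests on the assumed ICC, ρ and φ.

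**What to change.** In section E.2.b, schedule Session 2 approximately 7 days after Session 1. Keep 2-3 days between Sessions 2 to 5 and the existing 10-day exception. Align the consent form if it states the interval. As an optional clarification, define the baseline covariate in I.2 as a per-day rate. That would also help if enrolment has already begun, which the documents do not say, because participants would then have baselines of different lengths.

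The cost is one sentence and about 4-5 more days per participant (20-23 instead of 15-19 days from Session 1 to Session 6), within the planned 3 months. At three random prompts a day, that is 3 × (4 to 5) = 12-15 more prompts each.

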Abbreviated Title: *Lab/GMA drinking*

Version Date: 2/16/2022

Abbreviated Title: Lab/GMA drinking

Protocol #: 16-DA-N140

Version Date: 2/16/2022

Title: Effects of a new behavioral intervention on alcohol craving and drinking

NIH Principal Investigator: [name].

Branch: TAMB/RAPT Institute:

NIDA IRPBRC 01B602

[name]

[name]

[contact]

E-mail: [contact]

Abbreviated Title: Lab/GMA drinking

Version Date: 2/16/2022

A. Précis

Objective: To evaluate alcohol memory retrieval-extinction, a novel behavioral procedure for reduction of craving and drinking, in problem drinkers.

Study population: We will collect evaluable data from up to 75 participants. Participants are evaluable if they complete geographical momentary assessment (GMA, described below). All participants will be adult alcohol drinkers (men: > 14 drinks/week or > 4 drinks/day; women: > 7 drinks/week or > 3 drinks/day) whose drinking scores as hazardous on the Alcohol Use Disorders Identification Test. Participants will not be seeking treatment for an alcohol-use disorder, be physiologically dependent on alcohol, or have other drug use disorders.

Design: A randomized study with three groups. Participants will use smartphones to provide geotagged reports of alcohol craving and drinking in daily life (GMA reports) before, between, and after a series of laboratory sessions. During sessions, participants will drink an alcoholic beverage (individualized to produce a 0.06 g/dL blood alcohol content) or a soft drink. Participants will then be repeatedly presented with alcohol- or soft-drink-associated cues without further drinking. These are the memory retrieval and extinction portions, respectively, of memory retrieval-extinction. Previous studies suggest this procedure can robustly reduce Pavlovian associations between cues and responses such as craving. The mechanism seems to involve memory reconsolidation, in which freshly retrieved associations (e.g., “drink cues and consumption → pleasant effects”) become more vulnerable to disruption by extinction.

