Three groups will be tested: (1) alcohol retrieval / alcohol extinction will be compared to (2) soft-drink retrieval / alcohol extinction and (3) alcohol retrieval / soft-drink extinction. Before and after retrieval-extinction, participants will be tested for alcohol craving and cue-induced physiological responses in laboratory sessions. Retrieval-extinction will be followed by 1 week of “follow-up” GMA reporting, with telephone contact 30 days thereafter.

Outcome parameters: The co-primary outcome measures are: self-reported alcohol craving in the laboratory sessions before and after retrieval-extinction, and GMA reports of alcohol craving and drinking. Daily-life responses are important because the version of retrieval-extinction we will be using, with retrieval induced by drinking alcohol itself, rather than alcohol cues alone, may be especially likely to have effects that generalize from the laboratory to daily life. Secondary outcome measures are: (1) self-reported alcohol craving and drinking at 30-day follow-up, (2) physiological reactivity during sessions, and (3) urine biomarkers for alcohol consumption.

Abbreviated Title: Lab/GMA drinking

Version Date: 2/16/2022

B. Table of Contents

A. Précis.....	2
B. Table of Contents	3
C. Background	5
D. Study Objectives	11
E. Study Design and Methods	12
1. Study overview	12
2. Study procedures.....	13
3. Follow-up/termination procedures.....	26
F. Inclusion and Exclusion Criteria	26
1. Inclusion criteria	27
2. Exclusion criteria	28
G. Clinical and Laboratory Methods	29
H. Collection and Storage of Human Specimens or Data.....	29
I. Statistical Analysis	30
1. Outcome measures	30
2. Analysis of study outcomes	30
3. Criteria for significance	32
J. Required Sample Size	32
K. Plans for Enrollment at Multiple Sites.....	32
L. Human Subjects Protection Plan	33
1. The responsibilities of investigators	33
2. The names of investigators who will obtain informed consent.....	33
3. Rationale for subject selection based on gender/ethnic/race categories at risk	33
4. Recruitment plan	34
5. Justification for exclusion of vulnerable populations	36
6. Evaluation of Risks/Discomforts and Benefits ratio.....	36
7. Subject monitoring	39
8. Conflicts of interest.....	40
M. Protection of Participants' Privacy and Confidentiality.....	40
N. Study Agents/Interventions.....	42
O. Plan for Reporting Unanticipated Problems and Adverse Events	42
P. Data and Safety Monitoring	42
Q. Clinical Monitoring Plan	43

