- PhenX Toolkit Alcohol Specific Intermediate Phenotypes (ver. 13.1, www.phenxtoolkit.org): includes questionnaires on current alcohol craving, alcohol motives and expectancies, and acute subjective effects of alcohol.
- Penn Alcohol Craving Scale (Flannery et al., 1999): assesses alcohol craving on a week’s timescale, providing a retrospective measure of craving.
- Readiness to Change Questionnaire (Rollnick et al., 1992): assesses participants in terms of the “stages of change” (precontemplation, contemplation, action) regarding self-perceived excesses in drinking.
- Brief Situational Confidence Questionnaire (Breslin et al., 2000): measures participants’ confidence in their ability to resist drinking in different types of risky situation (e.g., social pressure, physical discomfort).
- Plymouth Sensory Imagery Questionnaire (Andrade et al., 2014): measures the vividness of participants’ ability to form mental images, in several sensory modalities.

Abbreviated Title: Lab/GMA drinking

Version Date: 2/16/2022

- Neighborhood Environment Walkability Scale (NEWS) (Saelens et al., 2003): an 82-item survey assessing types of residences, proximity to stores and facilities, access to services, aesthetic quality, safety from traffic and crime, and neighborhood satisfaction.
- Behavioral Inhibition System / Behavioral Activation System Scales (Carver & White, 1994): assesses reward processing in terms of appetitive motivation, which is based on the pursuit of reward, versus aversive motivation, which is based on the avoidance of punishment or nonreward.

Session 1: Cue-script development: We will collect information for developing personalized sets of alcohol-associated stimuli to be used in Sessions 2-6. Imagery scripts will be developed adapting the methods of Sinha and colleagues (2003), which we have previously used to study food craving and eating (protocol 475). Participants will be asked to identify and describe (1) a pleasant personal situation that involved drinking alcohol (alcohol-related script) and (2) a pleasant personal situation that did not involve drinking alcohol (alcohol-unrelated script). We will avoid use of situations with strong negative emotional valence and/or stressful content (e.g., being cited for driving under the influence), both of which can affect alcohol craving (Rubonis et al., 1994; Willner et al., 1998; Fox et al., 2007; Ray, 2011).

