Retrieval: Participants will be placed in one of the two rooms they visited in Session 1. They will first complete a rating of their craving for alcohol and soft drinks. They will then be provided with either a beverage that contains alcohol (alcohol retrieval condition) or does not (soft-drink retrieval condition). The alcohol-containing beverage will be selected based on the types (beer, wine, spirit) and brands (commercial packaging) of beverages consumed in the previous 90 days, assessed by the “most frequently consumed alcoholic beverage” questionnaire. The participant’s most frequently consumed beverage will typically be chosen for use during experimental sessions, but we will also discuss the results of the questionnaire with each participant to determine what he/she considers “typical” liked drinks for him/herself. A different beverage (i.e., not the most frequently consumed beverage) may be chosen from among these typical drinks if the participant’s most frequently consumed beverage is not easily commercially available (e.g., is homemade or not in current production) or not practicable for attaining the study’s target BAC in the time available for drinking in the session (e.g., a beverage that has a very low concentration of alcohol that would require a participant with a large volume of distribution rapidly to consume large volumes of liquid). The goal is to arrive with the participant at a beverage that (1) is acceptable to him/her to drink in the quantity required in the time available in the session and (2) provides a stimulus that is specific enough to the experience of the particular participants to be effective for memory retrieval and producing craving (Staiger & White, 1991). The soft drink will be based on participants’ reports collected in Session 1 of typical nonalcoholic beverages consumed and liked,

Abbreviated Title: Lab/GMA drinking

Version Date: 2/16/2022

screened by the experimenters to exclude caffeinated beverages and beverages commonly used by particular participants as mixers for alcohol.

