Participants will be given a volume of alcoholic beverage necessary to produce a BAC of 0.06 ± 0.01 g/dL. We will adjust the amount of alcohol administered to attain this BAC based on equations by Brick (2006, Formula 14). Participants will be weighed at the beginning of each session for determination of total body water (Brick 2006, Formula 10), which is needed for the alcohol dose adjustment. Participants who do not reach the expected BAC will proceed with the rest of the session, but when we analyze the study data, we will perform sensitivity analyses in which we see whether omitting their data changes the conclusions.

The volume of soft drink we give will be adjusted for each participant to match the caloric content of the participant's preferred alcoholic beverage.

To enhance retrieval, participants will be given their beverage along with an empty commercial package for that beverage; for example, Budweiser beer served in a pint glass along with an empty Budweiser can for alcohol retrieval, or Tropicana orange juice served in a tumbler alongside an empty Tropicana carton for soft-drink retrieval. To help standardize BAC during the subsequent extinction training, we will limit the time participants are given to finish the beverage, to a maximum of 40 min. The time each participant takes to finish the beverage will be recorded. If a participant finishes the beverage in less than 40 min, the extinction procedure can begin (i.e., we will not wait for the full 40 min to pass before initiating extinction). Before and 30 min after drinking, participants will complete the PhenX Measure: Acute Subjective Response to Substances questionnaire.

If a participant cannot or will not drink the whole beverage, we will measure the volume of beverage remaining undrunk. Participants who drink $\geq 66\%$ of the initial volume will be allowed to continue with the session. Participant who drink less will be considered not to have completed the retrieval procedure and will not proceed to the extinction procedure. Instead, they will be asked to wait for discharge from the laboratory, using the procedures for release described below. Given a failure to complete retrieval, a retrieval-extinction session can be rescheduled once; participants who do not complete the beverage second time will be discharged from the protocol.

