During extinction, participants will listen to audio recordings of the imagery scripts developed in Session 1. Participants receiving alcohol extinction will listen to their alcohol-related script; participants receiving soft-drink extinction will listen to their alcohol-unrelated script. Participants will also be given their preferred beverage along with empty commercial packaging; these will be the same during extinction as they were during retrieval, but during extinction, participants will not drink.

For all participants, cues will be presented in 5-min blocks: audio imagery scripts for 2 min, beverage exposure for 3 min. Once per min during the 3 min of beverage exposure, the participant will be instructed to take the glass in hand, raise it to his or her nose, and inhale its scent. Participants who drink any of the beverage during the extinction procedure will be discharged from the protocol.

There will be five blocks of cue presentation per session, with 5 min between blocks. In the time between blocks, the cues will be obscured from participants' view. Participants will fill out the one-item alcohol craving VAS if needed and will then be instructed to relax until the next block of cues. The alcohol craving VAS will be given three times during the extinction session: (1) immediately before the first block of cues, (2) immediately after the first block of cues, and (3) immediately after the fifth, final block of cues. The rating taken before the first block will be used to determine whether the beverage itself increased craving (Christiansen et al., 2013; Rose et al., 2014). To check that participants were successfully attending to the cues, following the last urge scale, participants may be asked brief open-

Abbreviated Title: Lab/GMA drinking

Version Date: 2/16/2022

ended questions about the session (e.g., “Tell me about what you did in today’s session...”). Participants will then be allowed to remain in the room and to relax for 20 min, at which point physiological monitoring will be ended, yielding a total extinction time of 65 min. During this period, participants will be given instructions to initiate progressive muscle relaxation and to focus on deep breathing, as after the script generation procedure. If participants are still feeling craving or otherwise “triggered” by the cues at the end of this period, they will receive counseling.

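### The extinction instructions tie the beverage and packaging to the retrieval condition for every group, which contradicts the definitions of both control groups

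*Combined protocol and SAP*

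**What the plan says.** All references are to the combined protocol and SAP.

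- **Group definitions.** Section A (Précis) names the two controls as "2) soft-drink retrieval / alcohol extinction and (3) alcohol retrieval / soft-drink extinction" and describes the extinction step thus: "Participants will then be repeatedly presented with alcohol- or soft-drink-associated cues without further drinking". Section E.1 repeats the definitions and adds that "the soft-drink retrieval condition is a no-alcohol retrieval condition, and the soft-drink extinction condition is a no-alcohol extinction condition". Section E.2 (Experimental groups and randomization) says that "Group 2 represents a traditional CET approach", without a relevant retrieval step.
- **Retrieval beverage.** Section E.2.b (Retrieval) gives each participant "either a beverage that contains alcohol (alcohol retrieval condition) or does not (soft-drink retrieval condition", and "participants will be given their beverage along with an empty commercial package for that beverage". Beverage and package therefore follow the retrieval assignment.
- **Extinction script.** Section E.2.b (Extinction) assigns the script by extinction condition: alcohol-related for alcohol extinction, alcohol-unrelated for soft-drink extinction. The second script is defined in section E.2.a as "a pleasant personal situation that did not involve drinking alcohol (alcohol-unrelated script"; it need not mention a soft drink.
- **Extinction beverage.** The same paragraph then says of the beverage and empty packaging that "these will be the same during extinction as they were during retrieval, but during extinction, participants will not drink". No group is excepted.
- **Exposure schedule.** Each cue block has 2 minutes of script and 3 minutes of beverage exposure. There are five blocks per session and four sessions.

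**The concern.** A rule that carries the retrieval beverage forward into extinction works only where the two conditions match, and by design they match in one arm of three. In the two control arms it gives participants the opposite beverage from the one their extinction label requires, while they hear the script that fits the label.

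The control arms carry the study's interpretation. Section E.2 uses them to ask whether the procedure needs both its components. Section I.2 rests that conclusion on the experimental group differing from both controls, and would read a difference from only one as evidence that both components were not required. If the sentence were followed exactly, Group 2 would not be a clean cue-exposure control and Group 3 would not be an alcohol-free extinction control. Neither would isolate the component that the inference needs.

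**Working it through.** The plan states no figure here that needs reproducing. The check applies the extinction-beverage sentence to each group, then counts the cue minutes affected.

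**Step 1. Apply the rule by group** (extinction beverage = retrieval beverage).

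| Group | Retrieval beverage | Assigned extinction | Extinction beverage as written | Conflict |
|---|---|---|---|---|
| 1, experimental | alcohol | alcohol | alcohol | no |
| 2, control A | soft drink | alcohol | soft drink | yes |
| 3, control B | alcohol | soft drink | alcohol | yes |

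**Step 2. Look for another passage that settles it.** The Study Timeline table in E.2 marks only that a beverage and packaging are present in extinction, not which ones. No other visible passage states the extinction beverage by group.

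**Step 3. Count the cue minutes** (block schedule from E.2.b, Extinction).

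- Blocks: 5 per session × 4 sessions = 20.
- Script: 20 × 2 = 40 min. Beverage: 20 × 3 = 60 min. Total: 40 + 60 = 100 min.
- Mismatched share in each control group: 60/100, or 3 of every 5 cue minutes (15 of 25 per session).

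| Cue minutes, Sessions 2-5 | Experimental | Group 2 | Group 3 |
|---|---|---|---|
| Alcohol cues, as written | 40 + 60 = 100 | 40 (script only) | 60 (beverage only) |
| Alcohol cues, by label | 100 | 40 + 60 = 100 | 0 |
| Soft-drink cues, as written | 0 | 60 | 0 |
| Soft-drink cues, by label | 0 | 0 | 60 |

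Only beverage time is counted as a soft-drink cue, because the alcohol-unrelated script is not defined as one. On the literal wording, Group 3's soft-drink extinction would contain no specified soft-drink cue at all.

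**The case against.** The strongest reply is that the sentence means the same individually chosen product, not the same assignment. Two products are selected for each participant: the Retrieval text describes choosing both an alcoholic beverage and a soft drink, and everyone receives both in the Session 6 reinstatement test. On this view the sentence asks only that brand, serving style and packaging stay constant. Context supports that intent. The preceding sentence splits the scripts by extinction condition, section E.2.c refers to earlier assignment to soft-drink cues, and the renewal test presents alcohol cues in the manner of the extinction sessions.

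It is also fair to say that:

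- the scripts remain correctly assigned, so even literally the cues would be mixed rather than swapped;
- the minute counts weigh script and beverage time equally, which the documents do not support;
- the group labels alone do not say which beverage is held in extinction, so the most direct clash is with the definition of soft-drink extinction in E.1;
- no deviation is shown.

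Much of this stands. The likely intent is clear, the wording looks like a drafting slip, and the counts are illustrative only. The alternative reading still does not rescue the sentence. It refers back to what was presented at retrieval, and there Group 2 is served no alcoholic beverage and Group 3 no soft drink. Neither control has the required product to carry forward. This is also the only visible instruction on which beverage to present in extinction, so it is an operative rule and not background text.

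**Conclusion.** The concern holds. The extinction-beverage sentence is wrong as written for two of the three groups and contradicts sections A, E.1 and E.2. The mismatch covers 60 of 100 cue minutes in each control group, if the sentence is read literally and script and beverage minutes are counted alike.

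No direction or size of bias is claimed, and no effect on power or effect size can be derived from the documents. Nothing shows that sessions were run on the literal wording. The appendices, and the checklists and SOP manuals mentioned in section R.1, may settle actual practice but are not available here. The point should be fixed: the intent can be inferred, but the text defines what two arms receive, and the study's main conclusion depends on those arms.

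**What to change.** 1. Reconcile the sentence in E.2.b (Extinction) with sections A, E.1 and E.2 by stating the extinction beverage and packaging for each of the three groups, so that they follow the extinction assignment as the script already does.
2. Confirm from existing session records which beverage was presented in extinction.
3. Only if any session followed the literal wording, report the number by group and add a sensitivity analysis for those sessions. Keep the primary analysis by randomised group.

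The cost is one protocol sentence and a check of existing records. It needs no extra visits, staff or participants.
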